15.2.3 Adverse Events leading to study discontinuation

Treatment emergent AEs leading to study discontinuation will be summarized by system organ class and preferred term displaying the number and percentage of patients with at least one AE recorded at each level of summarization. The total number of events leading to study discontinuation and the number and percentage of patients with at least one treatment emergent AE leading to study discontinuation will also be displayed.

15.2.4 Adverse Events by Severity

Treatment emergent AEs will be summarized by system organ class, preferred term and severity (mild, moderate, severe). The summarization will be performed for the total safety analysis set and for the pivotal sub group. The table will display the number and percentage of patients with at least one TEAE recorded at each level of summarization within the preferred term. The total number of events along with the number and percentage of patients with at least one treatment emergent AE will also be displayed by severity. In the event of missing severity information, the severity will be displayed as 'Missing'.

The same presentation will be displayed for treatment emergent SAEs.

15.2.5 Adverse Events by Relationship to Study Drug

Treatment emergent AEs will be summarized by system organ class, preferred term and relationship to study drug (related, unrelated). The summarization will be performed for the total safety analysis set and for the pivotal sub group. The table will display the number and percentage of patients with at least one drug-related TEAE recorded at each level of summarization. The total number of events along with the number and percentage of patients with at least one drug-related treatment emergent AE will also be displayed.

Treatment emergent adverse events as judged by investigator as possible, probable or definite will be classed as related. Those recorded as not related or unlikely will be classed as unrelated. In the event of missing relationship information, the relationship will be imputed as related.

SAEs will be summarized in the same way.

15.2.6 Deaths

Information on the number and percentage of patients reporting TEAEs leading to death will be included in the overview table described in Section 15.2. Information on each death will be summarized in individual patient narratives.

15.3 Laboratory data

Laboratory test results will be compared to reference ranges, and values outside of the applicable reference range will be flagged as high (H) or low (L). In the data listing clinically significant values will also be indicated.

Laboratory data will be summarized by parameter and visit with descriptive statistics for the total safety analysis set and the pivotal sub group. This summary will be repeated within baseline ADA positive and baseline ADA negative subgroups.

Laboratory test results categorized as in or outside of the applicable range will be summarized using shift tables and shift plots i.e. shift from Baseline.

The concentration/value for each laboratory parameter will be plotted against time using a spaghetti plot for each patient.

Laboratory data will be listed in full.

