The polypeptide sequence of SOBI003 is identical to human sulfamidase. However, as a result of use of the CHO expression system and the glycan modifications, through which some peripheral carbohydrate ring structures in the glycans are linearized, the overall structure of SOBI003 is not identical to human sulfamidase. Therefore, an immune reaction to SOBI003 may be expected in analogy to what occurs with other ERTs. ADAs and their impact on safety, PK and PD are monitored closely in this extension study.

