#### 7.5.4.3 Immunogenicity

Serum and CSF samples are collected for central laboratory analysis of SOBI003 ADAs by a validated immunoassay method (York Bioanalytical Solutions Limited, York, UK). Assays are being developed for assessment of neutralizing antibodies, both for antibodies inhibiting cellular uptake and for enzyme activity inhibiting antibodies (BioAgilytix, Hamburg, Germany). At each sampling occasion, a blood volume of 1.5 mL will be collected.

Serum samples are collected prior to start of SOBI003 infusion at Weeks 38, 52, 78 and 104, and during Early Termination. Triplicate aliquots are required for each sampling time point.

CSF samples (0.5 mL) are collected at Weeks 52 and 104.

If the dose of SOBI003 is adjusted in a patient, serum samples are collected prior to start of the first adjusted infusion and then prior to the 3rd adjusted infusion i.e., at 2 occasions per dose adjustment.

For patients with an ADA-positive serum sample, the following will also be determined in serum: ADA titer, IgG subclasses, and presence of NAb.

For patients with an ADA-positive CSF sample, the following will also be determined in CSF: ADA titer and presence of NAb.

Should any patient permanently discontinue SOBI003 treatment, then a serum sample will be collected 30 to 40 days after the last SOBI003 administration for ADA assessment. Should the sample be ADA-positive, then the ADA titer will be determined and ADA samplings will continue at approximately monthly basis until the ADA has disappeared or titers have stabilized at a lower level.

The impact of ADAs on the safety, tolerability, and PK of SOBI003 will be explored, as well as the potential impact on HS levels in CSF, serum and urine.

Sampling details are provided separately in the Study laboratory manual.

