The PK parameters will be listed for each patient and summarized for each IMP dose using descriptive statistics (the number of patients, arithmetic mean, standard deviation, standard error, coefficient of variation (CV) expressed as a percentage, geometric mean, geometric CV%, median, minimum, maximum). This summary will be repeated for PK parameters within baseline ADA positive and baseline ADA negative subgroups, within ADA positive at any postbaseline visit and ADA negative at all postbaseline visits.

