16.2 Immunogenicity

The analysis of immunogenicity will in general be based on the immunogenicity analysis set. However, exceptions are the analyses of PK by ADA status at baseline, which will be based on the PK analysis set, and the AE analysis with ADA-categorized AEs in section 15.2.1.

For immunogenicity, baseline ADA (pre-existing ADA) from the previous study will be used.

The following definitions will apply as defined in the harmonised terminology for immunogenicity (Shankar et al., 2014, “Assessment and Reporting of the Clinical Immunogenicity of Therapeutic Proteins and Peptides—Harmonized Terminology and Tactical Recommendations”, The AAPS Journal, DoI:10.1208/s12248-014-9599-2):

- Evaluable patient: A patients with at least one sample taken after IMP administration that is appropriate for ADA testing (with reportable result).
- ADA-positive sample: When ADA is detected in a sample, the sample is considered positive.
- Baseline ADA: pre-existing antibodies detected at baseline.
- Treatment induced ADA: de novo development following administration of IMP (i.e., formation of ADA any time after the initial IMP administration in a patient without pre-existing ADA).
- Treatment boosted ADA: Baseline ADA boosted to higher level following IMP administration (i.e., at any time after the initial IMP administration the ADA titer is greater than the baseline titer by a factor of four).
- ADA-positive patient: A patient with at least one treatment-induced or treatment-boostered ADA-positive sample at any time during the treatment or follow-up observation period.
- ADA-negative patient: A patient without a treatment induced or treatment-boostered ADA-positive sample during the treatment or follow-up observation period.
- Baseline ADA Positive Patient: Patient with ADA at baseline. Such patient can have treatment boostered ADA after dosing.

Note that the requirement for inclusion in the immunogenicity set of at least one post-dose ADA assessment means that all patients in the immunogenicity set are “evaluable patients”.

The immunogenicity data will be listed for each patient and individual patient plots of titer measurement over time presented. Titer measurements will be summarized by visit and time point using descriptive statistics by IMP dose and overall. Immunogenicity will be evaluated in regards antibody prevalence (pre-existing antibodies), antibody incidence, titer and boosting following dosing, impact on pharmacokinetics responses.

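### No planned laboratory summary uses post-baseline ADA status, so children who seroconvert on SOBI003 are pooled with never-positive children in the baseline ADA negative subgroup

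*SAP*

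**What the plan says.** SAP 15.3 summarizes laboratory data by parameter and visit for the safety set and the pivotal subgroup, and then adds: "This summary will be repeated within baseline ADA positive and baseline ADA negative subgroups". Shift tables and shift plots from baseline follow, with no ADA grouping. The section also plans a plot over time for each patient and parameter, and full listings.

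SAP 16.2 fixes the terms. "For immunogenicity, baseline ADA (pre-existing ADA) from the previous study will be used", and the definition reads "Baseline ADA: pre-existing antibodies detected at baseline". Treatment-induced ADA is the "formation of ADA any time after the initial IMP administration in a patient without pre-existing ADA".

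Two other parts of the SAP use on-treatment status. SAP 16.1 repeats the PK summaries by baseline ADA and also "within ADA positive at any postbaseline visit and ADA negative at all postbaseline visits". SAP 15.2.1 tabulates treatment-emergent adverse events by the patient's ADA status when the event occurred, and SAP 16.2 repeats that table by titer interval.

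The protocol states the aim in Section 7.5.4.3: "The impact of ADAs on the safety, tolerability, and PK of SOBI003 will be explored". Section 5.1.4 adds: "ADAs and their impact on safety, PK and PD are monitored closely in this extension study".

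**The concern.** The protocol's immunogenicity concern in this study is mainly antibody that develops under treatment. Protocol 5.1.4 says an immune response may be expected by analogy with other enzyme replacement therapies, and Protocol 7.5.1.9 puts ADA first when blood volume is short. The laboratory split instead uses a variable fixed before the first dose, which is two years old by Week 104.

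Laboratory safety variables are a secondary endpoint of the primary objective (Protocol 6.1.2, SAP 3.5.2). If ADA shifts a laboratory parameter, the planned summary would mix the affected children with unaffected ones in one subgroup. The other subgroup may be very small or empty. The SAP gives no reason for treating laboratory data differently from PK and adverse events.

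**Working it through.** The plan states no figure on this point, so the main check is of definitions.

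**1. Where seroconverters fall.** Treatment-induced ADA requires the absence of pre-existing ADA (SAP 16.2). The laboratory subgroups are defined by the presence or absence of pre-existing ADA (SAP 15.3). So 100% of children with treatment-induced ADA are in the baseline ADA negative subgroup and 0% in the other, at every visit and at any titer.

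**2. Comparison across SAP sections.**

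| Output | Baseline ADA | On-treatment ADA |
|---|---|---|
| PK parameters (16.1) | yes | yes: positive at any, or negative at all, post-baseline visits |
| Adverse events (15.2.1, 16.2) | not used as the split | yes: status at the event, and titer interval |
| Laboratory summaries (15.3) | yes | no |
| Laboratory shift tables (15.3) | no | no |

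**3. Whether the data exist.** Safety laboratory and ADA samples are both taken pre-infusion at Weeks 38, 52, 78 and 104 (Protocol Tables 5, 6 and 13; Section 7.5.4.3). That is four scheduled pairs per child. Early termination and the third infusion after a dose adjustment add more.

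**4. Dilution (illustration).** Let m be the size of the baseline ADA negative subgroup and k the number of seroconverters in it. A mean shift D confined to seroconverters appears in the subgroup mean as (k/m) × D. The documents give no seroconversion rate. Take 9 children, none positive at baseline, so m = 9:
- k = 2: 2/9 = 0.22 D
- k = 4: 4/9 = 0.44 D
- k = 7: 7/9 = 0.78 D
- k = 9: 9/9 = 1.00 D, with no seronegative group to compare against

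**5. How often the planned split is empty (illustration).** With baseline prevalence p and n children, P(no baseline-positive child) = (1 − p)^n. The documents do not give p, so the values below are assumed. The planned number of children is 9 to 12.

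| p (assumed) | n = 9 | n = 12 |
|---|---|---|
| 5% | 0.95^9 = 0.63 | 0.95^12 = 0.54 |
| 10% | 0.90^9 = 0.39 | 0.90^12 = 0.28 |
| 20% | 0.80^9 = 0.13 | 0.80^12 = 0.07 |

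When the positive subgroup is empty, the baseline-negative table simply repeats the overall table. These figures show only that the planned split may be uninformative. They do not measure how far seroconverters distort the negative subgroup.

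**The case against.** The strongest reply is that little is hidden in 9 to 12 children. Laboratory data are listed in full and plotted per patient (SAP 15.3), and titers are listed and plotted per patient (SAP 16.2), so the two can be read together. Clinically significant laboratory values are to be reported as adverse events (Protocol 7.5.4.2), which brings them into the tables by ADA status and by titer interval. Protocol 9.4.7.4 promises only flags, listings and descriptive statistics for laboratory data. SAP Section 2 allows further exploratory analyses.

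Most of this stands, and it rules out three stronger readings that a reader might infer:
- That an ADA effect on laboratory safety cannot be seen at all. The individual outputs and the adverse event tables give two routes to it.
- That seroconverters are counted as ADA negative. The label is baseline ADA negative, and SAP 16.2 still classes a child with treatment-induced ADA as an ADA-positive patient.
- That the protocol's aim on ADAs and safety is abandoned. The protocol says the impact will be explored and does not promise a laboratory split. The adverse event analyses serve that aim.

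The reply does not close the gap. Under Protocol 7.5.4.1.1 an abnormal test becomes an adverse event only if it has symptoms (and then the symptom is recorded), leads to an intervention, or is judged clinically significant. Smaller systematic shifts do not enter by that route. The planned overlay figures combine titer with adverse events, not with laboratory values. Reading listings side by side is not a pre-specified analysis.

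It is also fair to say that a new split has thin cells. A boosted group needs a baseline-positive child, so it is empty at least as often as the baseline-positive group. If nearly all children seroconvert, the negative group almost disappears.

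**Conclusion.** The point holds as an inconsistency that is cheap to correct. No planned laboratory summary or shift table uses post-baseline ADA status, and the baseline ADA negative subgroup mixes children with treatment-induced ADA and children who were never positive. This follows from the SAP's definitions and rests on no assumption. It departs from the SAP's handling of PK and adverse events and fits poorly with the protocol's interest in ADAs and safety.

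What is lost is a grouped, pre-specified view of laboratory shifts that do not become adverse events. No hypothesis test, estimand or power statement is affected. The size of the dilution and the chance of an empty subgroup depend on ADA rates that the documents do not give, so the figures above are illustrations only.

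**What to change.** In SAP 15.3, add one of these groupings to the laboratory summaries and the shift tables:
- the split already used for PK in SAP 16.1: ADA positive at any post-baseline visit versus negative at all post-baseline visits; or
- ADA status at the paired pre-infusion sample (negative, treatment-induced, boosted).

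State the number of children and samples in each group. Add plots of laboratory values against concurrent titer, which remain readable if nearly all children seroconvert. The baseline split can stay beside these.

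The cost is SAP wording and regrouped tables from samples already scheduled. Cells will be small, and under the paired-sample option a child can contribute to more than one state, so the output should be labelled descriptive, with no tests.

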15.4 Vital signs

Vital signs (blood pressure, heart rate, body temperature, respiratory rate and pulse oximetry)) are measured at the time points specified in the study schedule of events.

Observed and changes from baseline in vital signs will be summarized by visit with descriptive statistics for the total safety analysis set and the pivotal sub group.

The vital signs will be plotted using spaghetti plots as described for the laboratory data except without boundaries for normal ranges.

Vital signs results will be listed in full.

16 Pharmacokinetics and Immunogenicity

Blood sampling for PK, PD and immunogenicity is undertaken at the time-points specified in the study schedule of assessments.

16.1 Pharmacokinetic Parameters

The PK analysis will be based on the PK analysis set.

Serum concentrations will be listed and summarised by time point. Individual serum concentration profiles will be plotted both on the original scale and on the log scale. Mean (\pm SD) and median serum concentration profiles will be plotted for each dose both on the original scale and on the log scale. The individual serum concentration data, and the actual time for IMP administration and blood sampling will be used in the derivation of the PK parameters.

PK calculations, based on serum concentrations, will be performed in Phoenix WinNonlin by means of NCA. The following multiple-dose PK parameters will be determined for SOBI003 at Weeks 39, 52, 78 and 104, and during dose-adjustments:

- The time of the end of the infusion of SOBI003, tEnd of inf
- The observed serum concentration at the end of infusion of SOBI003, CEnd of inf
- The observed serum concentration immediately before the start of infusion of SOBI003, CPre-dose
- The area under the plasma concentration-time curve from time 0 to last sample, AUC168h
- Clearance, CL

AUC168h will be calculated according to the linear log trapezoidal method. Other PK parameters may be calculated as applicable.

In addition to evaluating SOBI003 PK based on SOBI003-002 data only, PK of SOBI003 will also be evaluated based on study SOBI003-002 together with PK data obtained from study SOBI003-001, since administration of SOBI003 have been started in study SOBI003-001 for all patients.

Pre-dose SOBI003 concentrations in study SOBI003-002 will be used to explore if steady-state is maintained or if SOBI003 serum concentrations decrease or increase following totally 2 years administration of SOBI003. The extent of accumulation of SOBI003 serum concentrations during 2 years treatment will be explored by calculating accumulation ratio (Rac) based on PK data from both study SOBI003-001 and study SOBI003-002. Rac will be calculated as $AUC_{0-168h} \text{ week } n / AUC_{0-168h} \text{ week } 1$, where n is 38, 52, 78 and 104.

The ratio of peripheral/central serum concentrations of SOBI003 may be explored in study SOBI003-002, in case SOBI003 serum concentrations have been determined in this study, depending on the outcome of study SOBI003-001.

The effect of eg. dose-level, age or body-weight on SOBI003 PK will be explored eg. by plotting PK parameters versus dose, age, body-weight.

The PK parameters will be listed for each patient and summarized for each IMP dose using descriptive statistics (the number of patients, arithmetic mean, standard deviation, standard error, coefficient of variation (CV) expressed as a percentage, geometric mean, geometric CV%, median, minimum, maximum). This summary will be repeated for PK parameters within baseline ADA positive and baseline ADA negative subgroups, within ADA positive at any postbaseline visit and ADA negative at all postbaseline visits.

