The lowest SOBI003 serum exposures at the NOAEL dose levels in these species were observed in the mice following the 300 mg/kg dose, where mean  $C_{max,ss}$  was 86.3 and 163  $\mu\text{mol/L}$  and mean  $AUC_{\tau,ss}$  was 718 and 934  $\mu\text{mol}\cdot\text{h/L}$  in in male and female mice, respectively. Based on predicted steady state PK in patients ( $C_{max,ss}$  0.89, 3.0, and 5.9  $\mu\text{mol/L}$ ;  $AUC_{\tau,ss}$  11.5, 38.5, and 77.0  $\text{h}\cdot\mu\text{mol/L}$  at dose levels 3, 10 and 20 mg/kg), the margins to SOBI003 exposure in the pivotal toxicity studies are thus at least 100-fold for a starting dose of 3 mg/kg and at least 10-fold for a dose of 20 mg/kg. Further details are presented in the SOBI003 [Investigator Brochure](#)).

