## **7 Investigational plan**

### **7.1 Overall study design and plan**

This is an open, single-arm, multicenter extension study to assess the long-term safety, tolerability and efficacy of SOBI003 in pediatric MPS IIIA patients who previously participated in the FIH study ([SOBI003-001](#)) study. Patients completing the 24-week treatment of the FIH study will be offered to participate in the continuous 80 week treatment period of the extension study. The extension study starts with enrolment at Week 25, giving a total SOBI003

treatment duration of 104 weeks for each patient. Please refer to Figure 1 for an overview of the study design. A recent NH study is used as external control (22) to enable an evaluation of efficacy. Neurocognitive and adaptive behavior data assessed in the extension study at Week 52 and Week 104 following start of treatment will be compared to available NH data within the target study population. The NH population for comparison consists of 14 patients with a rapid progressive MPS IIIA disease and a baseline age of 12 to 72 months.

As the FIH study ([SOBI003-001](#)) has a sequential, ascending, multiple-dose design, the first patients will enter the extension study before the FIH study is completed. When entering the extension study, these patients will receive the highest dose that has been declared safe by the SRC in the ongoing FIH study ([SOBI003-001](#)) study. Patients enrolled in Cohort 1 of FIH study may thus be switched to the dose applied in Cohort 2 or Cohort 3, depending on safety clearance by the SRC. If a patient is initially switched to the dose applied in Cohort 2, the patient may subsequently later be switched to the dose applied in Cohort 3. Depending on recruitment rate in the FIH study ([SOBI003-001](#)) study, a patient enrolled in Cohort 1 may be directly switched to the dose applied in Cohort 3. Upon completion of the FIH study, an analysis aimed at selecting the dose for forthcoming studies will take place. Once the dose has been selected, this dose will be applied to all patients enrolled in the extension study.

[figure not shown]

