**Table 1 Minimum hospitalization periods**

Week	Minimum hospitalization period*
25 to 51, 53 to 103	Admission; day of infusion Discharge; 1 hour or later after the end of each infusion
52 and 104	Admission; day of infusion Discharge; 1 hour or later after the end of infusion
At week(s) of dose adjustments	Admission; day of infusion Discharge; 48 hours after initiation of each of the first 3 infusions**

\* Extended as per local routine for admission/discharge and per patient need as determined by the investigator (eg, concurrent illness, travel distance etc)

\*\* If dose adjustment is a decrease in dose as a result of study dose selection for forthcoming studies, and there are no safety concerns, the patient may be discharged 1 hour or later after the end of each infusion.

An emergency card containing details on how to seek medical help will be provided to each parent/caregiver and they will be instructed to always carry the emergency card. The card will also contain brief details on the study treatment and contact details to site staff in order to secure appropriate medical management of any emergency situation that has to be managed outside the study site.

Depending on the distance and any travelling difficulties, the regular weekly infusions of SOBI003 may be administered at home by a trained study nurse or at a geographically closer satellite site, if judged safe by the investigator and Sobi MD. At weeks with scheduled laboratory or efficacy assessments and during 12 weeks following a dose increase or reduction due to safety, SOBI003 infusions will always be performed at the PI site. If the patient receives all infusions at the PI site, they and their parent(s) may be relocated for parts the study or for the full study duration. The families are reimbursed for travel and, if applicable, for accommodation expenses and caregiver meals. Appointed study coordinators will assist the families with travel and accommodation arrangements.

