The drug accountability records will capture sufficient details to verify the amount of SOBI003 administered at each infusion occasion.

In case of occurrence of infusion reactions, the infusion duration may be prolonged up to 24 hours at the discretion of the investigator.

For individual study patients there may be situations, due to safety or infusion related reactions observed at a higher dose level, where it is judged by investigator that it is in the patient's best interest to reduce the treatment dose. In such situations investigator should discuss with Sobi MD regarding an individual patient dose adjustment.

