#### **7.5.1.7 Weeks of dose adjustments**

During the study there may be situations where individual patients or all study patients will increase or reduce their treatment dose, please refer to 7.4.4 and 7.4.5 for more details. In such situations, a more extensive initial schedule of assessments will follow.

Dose adjustments will be avoided during Weeks 48 to 52 and 100 to 104, in order not to interfere with study efficacy assessments on Week 52 and 104, respectively. Any requested dose adjustment during this time should be postponed until after these assessments have been completed, if not considered medically justified by the investigator.

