4.1 Overall study design and plan

This is an open, single-arm, multicenter extension study to assess the long-term safety, tolerability and efficacy of SOBI003 in pediatric MPS IIIA patients who previously participated in the (FIH) SOBI003-001 study. Patients completing the FIH study will be offered to participate in the extension study. Please refer to Figure 1 for an overview of the study design. A published natural history study (referred to as the NH study in the present document) is used as external control (**Error! Reference source not found.**). Neurocognitive and adaptive behavior data assessed in the extension study at Week 52 and Week 104 following start of treatment will be compared to available natural history data within the target study population. The natural history population for comparison consists of 14 patients with a rapid progressive MPS IIIA disease and a baseline age of 12 to 72 months.

[figure not shown]
As the FIH study has a sequential, ascending, multiple-dose design, the first patients will enter the extension study (SOBI003-002) before finalization of the FIH study. When entering the extension study, these patients will receive the highest dose that has been declared safe by the

SRC in the ongoing FIH study. Patients enrolled in Cohort 1 of FIH may thus be switched to the dose applied in Cohort 2 or Cohort 3, depending on safety clearance by the SRC. If a patient is initially switched to the dose applied in Cohort 2, the patient may subsequently later be switched to the dose applied in Cohort 3. Depending on recruitment rate in the FIH study, a patient enrolled in Cohort 1 may be directly switched to the dose applied in Cohort 3. Upon completion of the FIH study, an analysis aimed at selecting the dose for forthcoming studies will take place. Once the dose has been selected, this dose will be applied to all patients enrolled in the extension study. The Baseline in SOBI003-001 will be used as the baseline for SOBI003-002 (Figure 1).

SOBI003 is administered as weekly i.v. infusions over a period of time of 1 to 4 hours. Prior to initiation of each infusion, the patients are pretreated with a single dose of non-sedative antihistamine. If infusion-related reactions occur, then the infusion duration may be expanded up to 24 hours and supportive medication may be administered, at the discretion of the investigator.

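### The accumulation ratio in SAP 16.1 has no dose term, so after any dose change it mixes the dose ratio with accumulation

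*SAP*

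**What the plan says.** SAP 16.1 gives the purpose of Rac: "The extent of accumulation of SOBI003 serum concentrations during 2 years treatment will be explored by calculating accumulation ratio (Rac) based on PK data from" SOBI003-001 and SOBI003-002 together. It defines Rac as AUC0-168h at Week n over AUC0-168h at Week 1, for n = 38, 52, 78 and 104. It gives no dose term and does not limit Rac to visits at the Week 1 dose. The protocol does not define Rac.

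Week 1 belongs to the first-in-human study, where each patient receives a cohort dose. Both documents foresee later changes:

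- Protocol 7.1, on entry to the extension: "Patients enrolled in Cohort 1 of FIH study may thus be switched to the dose applied in Cohort 2 or Cohort 3".
- SAP 4.1, after dose selection: "Once the dose has been selected, this dose will be applied to all patients enrolled in the extension study".
- Protocol Table 1 provides for reductions: "If dose adjustment is a decrease in dose as a result of study dose selection for forthcoming studies".
- Protocol 7.5.1.7: "During the study there may be situations where individual patients or all study patients will increase or reduce their treatment dose".

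On reporting, SAP 16.1 says "The PK parameters will be listed for each patient and summarized for each IMP dose using descriptive statistics" and plans plots of PK parameters against dose. Clearance is a separate listed PK parameter.

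**The concern.** An accumulation ratio compares exposure late in treatment with exposure after the first dose, on the same dose. Here the numerator and denominator can come from different doses. A dose increase would then read as accumulation, and a decrease as loss of exposure.

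This is likely to arise in practice. Protocol 5.1.5 says the first-in-human study tests three dose levels. If all three contribute patients, one common dose can match the Week 1 dose of at most one level. A switch at Week 25 comes before all four Rac visits.

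The error can also hide a real effect. Protocol 5.1.4 says anti-drug antibodies and their impact on PK are to be monitored closely, and reports a possible antibody effect on AUC in monkeys. A true fall in exposure that coincides with a dose increase could give a Rac near 1.

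**Working it through.** The plan states no numerical Rac, so there is no figure to reproduce. The check is algebra plus the protocol's predicted exposures.

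**Inputs** (Protocol 5.1.3, "at dose levels 3, 10 and 20 mg/kg"): predicted steady-state AUC of 11.5, 38.5 and 77.0 h·µmol/L.

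**Formula.** Let A be true accumulation at constant dose. Under linear kinetics, Rac = (Dose_n / Dose_1) × A.

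**Linearity of the inputs.** AUC per mg/kg is 11.5/3 = 3.83, 38.5/10 = 3.85 and 77.0/20 = 3.85. The predictions are dose-proportional to within about 0.5%.

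**Rac with no true accumulation.** The predicted AUCs stand in for both weeks:

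| Change in dose (mg/kg) | AUC ratio | Rac as defined | Dose ratio | Dose-normalised Rac |
|---|---|---|---|---|
| 3 to 10 | 38.5/11.5 | 3.35 | 3.33 | 1.00 |
| 3 to 20 | 77.0/11.5 | 6.70 | 6.67 | 1.00 |
| 10 to 20 | 77.0/38.5 | 2.00 | 2.00 | 1.00 |
| 20 to 10 | 38.5/77.0 | 0.50 | 0.50 | 1.00 |

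The small gaps between 3.35 and 3.33, and between 6.70 and 6.67, come from dividing rounded AUCs.

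**Range for true accumulation.** The documents give no half-life, so A is unknown. If A lies between 1.0 and 2.0, a 10 to 20 change gives Rac of 2.0 to 4.0, and a 20 to 10 change gives 0.5 to 1.0. The first range overstates accumulation. The second turns accumulation into apparent loss or no change.

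**A masked loss (hypothetical).** Suppose exposure halves after a 10 to 20 change. Then Rac = (0.5 × 77.0)/38.5 = 1.0, which reads as no change. Dose/AUC goes from 20/77.0 = 0.26 to 20/38.5 = 0.52 mg/kg per h·µmol/L, so clearance doubles.

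**Whether summaries by dose repair it.** Patients on one current dose can have different Week 1 doses. As an illustration, take equal numbers from each of the three levels and no accumulation:

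- All at 20 mg/kg: mean Rac = (6.70 + 2.00 + 1.00)/3 = 3.23; geometric mean = (6.696 × 2.000 × 1.000)^(1/3) = 2.37.
- All at 10 mg/kg: mean Rac = (3.35 + 1.00 + 0.50)/3 = 1.62; geometric mean = (3.348 × 1.000 × 0.500)^(1/3) = 1.19.

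Dose-normalised, the mean is 1.00 in both cases. Grouping by current dose therefore leaves the problem in place.

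**The case against.** The strongest case is that this matters little. Rac is not a listed endpoint; the SAP only says accumulation will be explored with it. It enters no test and no dosing rule. Clearance, which is a listed endpoint and accounts for dose, is derived at essentially the same visits. SAP 15.1 requires dose-by-time graphs for every patient, covering both studies, and PK parameters are listed per patient. With 9 to 12 patients planned, a careful reader could trace an odd Rac to a dose change. SAP 16.1 also allows other PK parameters to be added, which would permit a normalised ratio. All of this stands, and it limits the consequence. None of it corrects the ratio or commits the sponsor to a corrected one.

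The sizes are also open to challenge. Protocol 7.4.4, on dose selection, is listed in the contents but is not in the text available for review. The lack of a link between doses and cohorts is therefore no fault of the plan. Cohort sizes, the selected dose and the number of patients changing dose are unknown as well, so the figures are illustrations, not estimates. The mechanism does not depend on them: with non-linear kinetics Rac would still carry a dose effect, though not exactly the dose ratio.

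Finally, an unchanged dose removes the dose ratio but not every source of difference. Protocol Table 10 adds a Day 2 sample at Weeks 52 and 104 that Weeks 38 and 78 lack, and infusion time may shorten from 4 hours to 1 hour. That is a separate caution and no defence of the formula.

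**Conclusion.** The concern holds. As written, at any visit where a patient's dose differs from the Week 1 dose, Rac reports the dose change together with any accumulation. For the dose pairs shown, the distortion runs from a factor of 0.50 to 6.70. This rests on assumed cohort doses of 3, 10 and 20 mg/kg, linear kinetics, and predicted steady-state AUCs standing in for Week 1.

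The scope is narrow. Rac is unaffected by this problem where the dose has not changed. The primary endpoint, the hierarchical tests and the clearance results are untouched, and the PK summaries by antibody status could still reveal a loss of exposure through other parameters. The pre-dose steady-state check uses SOBI003-002 data only, so it is affected only if a dose changes within the extension's PK sampling period. It is still worth correcting, because Rac cannot serve its stated purpose in the patients whose dose changes.

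**What to change.** Amend SAP 16.1 to define Rac = (AUC0-168h at Week n / actual dose at Week n) / (AUC0-168h at Week 1 / actual dose at Week 1), with dose in mg/kg. State that the mg/kg value is the amount given divided by the body weight used to set that week's dose. List both doses beside each Rac, and show the unnormalised ratio only for visits at the Week 1 dose. Interpret Rac together with clearance. Dose-normalise pre-dose concentrations only for patients whose dose changes within the extension's PK sampling period.

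The cost is a short SAP edit and a simple derivation. The dosing text of Protocol 7.4 already says "The drug accountability records will capture sufficient details to verify the amount of SOBI003 administered at each infusion occasion", and weight is taken every four weeks to set the dose. The one drawback is that normalising assumes dose proportionality, which the planned plots of PK parameters against dose can check. The change concerns a calculation only and implies nothing about which dose should be given.
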